Appendix 2. Criteria for Response Assessment

Changes: A more comprehensive description of the criteria for response assessment in lymphoma has been provided to ensure appropriate evaluation of patients with both FDG-avid and FDG-non-avid lymphoma subtypes and patients who are followed by PET/CT or by diagnostic CT. The criteria are consistent with Cheson 2014.

The criteria for response assessment in CLL have been updated and clarified consistent with both the Hallek 2008 and Cheson 2012 references.

Table 7: Revised Criteria for Response Assessment

Response and Site	PET CT Based Response	CT Based Response
Complete	Complete metabolic response	Complete radiologic response (all of the following)
Lymph nodes and extralymphatic sites	Score 1, 2, or 3 *with or without a residual mass on 5PS †	Target nodes/nodal masses must regress to ≤ 1.5 cm in Ldi
	It is recognized that in Waldeyer's ring or extranodal sites with high physiologic uptake or with activation within spleen or marrow (e.g., with chemotherapy or myeloid colony stimulating factors), uptake may be greater than normal mediastinum and/or liver. In this circumstance, complete metabolic response may be inferred if uptake at sites of initial involvement is no greater than surrounding normal tissue even if the tissue has high	No extralymphatic sites of disease

Version 9, 18 Feb 2020

Response and Site	PET CT Based Response	CT Based Response			
	physiologic uptake				
Nonmeasured lesion	Not applicable	Absent			
Organ enlargement	Not applicable	Regress to normal			
New lesions	None	None			
Bone marrow	No evidence of FDG avid disease in marrow	Normal by morphology; if indeterminate, IHC negative			
Partial Partial	Partial metabolic response	Partial remission (all of the following)			
Lymph nodes and extralymphatic sites	Score 4 or 5† with reduced uptake compared with baseline and residual mass(es) of any size	≥50% decrease in SPD of up to 6 target measurable nodes and extranodal sites			
-	At interim, these findings suggest responding disease	When a lesion is too small to measure on CT, assign 5 mm × 5 mm as the default value			
-	At end of treatment, these findings indicate residual disease	When no longer visible, 0 × 0 mm			
-		For a node > 5 mm × 5 mm, but smaller than normal, use actual measurement for calculation			
Nonmeasured lesions	Not applicable	Absent/normal, regressed, but no increase			
Organ enlargement	Not applicable	Spleen must have regressed by > 50% in length beyond normal			
New lesions	None	None			
Bone marrow	Residual uptake higher than uptake in normal marrow but reduced compared with baseline (diffuse uptake compatible with reactive changes from chemotherapy allowed). If there are persistent focal changes in the marrow in the context of a nodal response, consideration should be given to further evaluation with MRI or biopsy or an interval scan	Not applicable			
No response or stable disease	No metabolic response	Stable disease			
Target nodes/nodal masses, extranodal lesions	Score 4 or 5 with no significant change in FDG uptake from baseline at interim or end of treatment	<50% decrease from baseline in SPD of up to 6 dominant, measurable nodes and extranodal sites; no criteria for progressiv disease are met			
Nonmeasured lesions	Not applicable	No increase consistent with progression			
Organ enlargement	Not applicable	No increase consistent with progression			
New lesions	None	None			
Bone marrow	No change from baseline	Not applicable			
Progressive disease	Progressive metabolic disease	Progressive disease requires at least 1 of the following			
Individual target nodes/nodal masses	Score 4 or 5 with an increase in intensity of uptake from baseline and/or	PPD progression:			
Extranodal lesions	New FDG avid foci consistent with lymphoma at interim or end of treatment assessment	An individual node/lesion must be abnormal with:			
		Ldi > 1.5 cm and			
		Increase by ≥ 50% from PPD nadir and			
		An increase in Ldi or Sdi from nadir			
		0.5 cm for lesions ≤ 2 cm			
		1.0 cm for lesions > 2 cm			
		In the setting of splenomegaly, the spleni length must increase by > 50% of the extent of its prior increase beyond baseling (e.g., a 15 cm spleen must increase to > 100 cm.			

Version 9, 18 Feb 2020

Response and Site	PET CT Based Response	CT Based Response
		cm). If no prior splenomegaly, must increase by at least 2 cm from baseline
		New or recurrent splenomegaly
Nonmeasured lesions	None	New or clear progression of preexisting nonmeasured lesions
New lesions	New FDG avid foci consistent with lymphoma rather than	Regrowth of previously resolved lesions
	another etiology (e.g., infection, inflammation). If uncertain regarding etiology of new lesions, biopsy or interval scan may	A new node > 1.5 cm in any axis
	be considered	A new extranodal site > 1.0 cm in any
		axis; if < 1.0 cm in any axis, its presence
		must be unequivocal and must be attributable to lymphoma
		Assessable disease of any size unequivocally attributable to lymphoma
Bone marrow	New or recurrent FDG avid foci	New or recurrent involvement

* A score of 3 in many patients indicates a good prognosis with standard treatment, especially if at the time of an interim sean. However, in trials involving PET where de escalation is investigated, it may be preferable to consider a score of 3 as inadequate response (to avoid under treatment). Measured dominant lesions: Up to 6 of the largest dominant nodes, nodal masses, and extranodal lesions selected to be clearly measurable in 2 diameters. Nodes should preferably be from disparate regions of the body and should include, where applicable, mediastinal and retroperitoneal areas. Non nodal lesions include those in solid organs (e.g., liver, spleen, kidneys, lungs), GI involvement, cutaneous lesions, or those noted on palpation. Nonmeasured lesions: Any disease not selected as measured, dominant disease and truly assessable disease should be considered not measured. These sites include any nodes, nodal masses, and extranodal sites not selected as dominant or measurable or that do not meet the requirements for measurability but are still considered abnormal, as well as truly assessable disease, which is any site of suspected disease that would be difficult to follow quantitatively with measurement, including pleural effusions, ascites, bone lesions, leptomeningeal disease, abdominal masses, and other lesions that cannot be confirmed and followed by imaging. In Waldeyer's ring or in extranodal sites (e.g.,, GI tract, liver, bone marrow), FDG uptake may be greater than in the mediastinum with complete metabolic response, but should be no higher than surrounding normal physiologic uptake (e.g., with marrow activation as a result of chemotherapy or myeloid growth factors).

† PET 5PS: 1, no uptake above background; 2, uptake ≤ mediastinum; 3, uptake > mediastinum but ≤ liver; 4, uptake moderately > liver; 5, uptake markedly higher than liver and/or new lesions; X, new areas of uptake unlikely to be related to lymphoma.

Abbreviations: 5PS, 5 point scale; CT, computed tomography; FDG, fluorodeoxyglucose; IHC, immunohistochemistry; Ldi, longest transverse diameter of a lesion; MRI, magnetic resonance imaging; PET, positron emission tomography; PPD, cross product of the Ldi and perpendicular diameter; Sdi, shortest axis perpendicular to the Ldi; SPD, sum of the product of the perpendicular diameters for multiple lesions.

Source: Cheson 2014.

Response Assessment of CLL (Source: Hallek 2008)

The World Health Organization (WHO) classification of hematopoietic neoplasias describes CLL as leukemic, lymphocytic lymphoma, being only distinguishable from small lymphocytic lymphoma (SLL) by its leukemic appearance. In the World Health Organization classification, CLL is always a disease of neoplastic B cells, whereas the entity formerly described as T cell chronic lymphocytic leukemia (T CLL) is now called T cell prolymphocytic leukemia.

It is important to verify that the subject has CLL and not some other lymphoproliferative disease that can masquerade as CLL, such as hairy cell leukemia, or leukemic manifestations of mantle cell lymphoma, marginal zone lymphoma, splenic marginal zone lymphoma with circulating

Version 9, 18 Feb 2020

villous lymphocytes, or follicular lymphoma. To achieve this, it is essential to evaluate the blood count, blood smear, and the immune phenotype of the circulating lymphoid cells.

Definition of Response

Assessment of response should include a careful physical examination and evaluation of the blood and marrow (See **). To define a CR, the marrow sample must be at least normocellular for age, with less than 30% of nucleated cells being lymphocytes. Lymphoid nodules should be absent.

Complete remission (CR)

CR requires all of the following criteria as assessed at least 2 months after completion of therapy:

- Peripheral blood lymphocytes (evaluated by blood and differential count) below 4×10^9 /L (4.000/uL).
- 13. In clinical trials, the presence of MRD after therapy should be assessed. The sensitivity of the method used to evaluate for MRD should be reported.
- 14. Absence of significant lymphadenopathy (e.g, lymph nodes > 1.5 cm in diameter) by physical examination. In clinical trials, a CT scan of the abdomen, pelvis, and thorax is desirable if previously abnormal. Lymph nodes should not be larger than 1.5 cm in diameter.
- 15. No hepatomegaly or splenomegaly by physical examination. In clinical trials, a CT scan of the abdomen should be performed at response assessment if found to be abnormal before therapy or if physical examination is inconclusive at the time of evaluation.
- 16. Absence of constitutional symptoms.
- 17. Blood counts above the following values:
 - Neutrophils More Than $1.5 \times 10^9/L$ ($1500/\mu L$) without need for Exogenous Growth Factors.
 - Platelets More Than $100 \times 10^9/L$ ($100,000/\mu L$) without need for Exogenous Growth Factors
 - Hemoglobin More Than 110 G/L (11.0 g/dL) without Red Blood Cell Transfusion or need for Exogenous Erythropoietin.
 - For subjects in clinical trials a marrow aspirate and biopsy should be performed at least 2 months after the last treatment and if clinical and laboratory results above demonstrate that a CR has been achieved

Partial remission (PR)

PR is defined by the criteria described in Sections 1, 2, or 3 below (if abnormal before therapy), as well as one or more of the features listed in Section 4. To define a PR, these parameters need to be documented for a minimal duration of 2 months (See Table 8). Constitutional symptoms persisting for more than 1 month should be recorded.

- 1. A decrease in the number of blood lymphocytes by 50% or more from the value before therapy.
- 18. Reduction in lymphadenopathy (by CT scans in clinical trials or by palpation in general practice) as defined by the following:
 - A decrease in lymph node size by 50% or more either in the sum products of up to 6 lymph nodes, or in the largest diameter of the enlarged lymph node(s) detected prior to therapy.
 - No increase in any lymph node, and no new enlarged lymph node. In small lymph nodes (< 2 cm), an increase of less than 25% is not considered to be significant.
- 19. A reduction in the noted pretreatment enlargement of the spleen or liver by 50% or more, as detected by CT scan (in clinical trials) or palpation (in general practice).
- 20. The blood count should show one of the following results:
 - Neutrophils more than 1.5 x 10^9 /L (1,500/ μ L) without need for exogenous growth factors.
 - Platelet counts greater than 100×10^9 /L $(100,000/\mu\text{L})$ or 50% improvement over baseline without need for exogenous growth factors.
 - Hemoglobin greater than 110 g/L (11.0 g/dL) or 50% improvement over baseline without requiring red blood cell transfusions or exogenous erythropoietin.

Stable disease (SD)

Patients who have not achieved a CR or a PR, and who have not exhibited progressive disease, will be considered to have stable disease (which is equivalent to a nonresponse).

Progressive Disease

Progressive disease during or after therapy is characterized by at least one of the following:

- 1. Lymphadenopathy.
 - Progression of lymphadenopathy is often discovered by physical examination and should be recorded. In CLL, the use of CT scans usually does not add much information for the detection of progression or relapse. Therefore, the use of imaging methods to follow CLL progression is at the discretion of the treating physician. Disease progression occurs if one of the following events is observed:
 - Appearance of any new lesion, such as enlarged lymph nodes (> 1.5 cm), splenomegaly, hepatomegaly, or other organ infiltrates.
 - An increase by 50% or more in greatest determined diameter of any previous site.
- 21. An increase in the previously noted enlargement of the liver or spleen by 50% or more or the de novo appearance of hepatomegaly or splenomegaly.
- 22. An increase in the number of blood lymphocytes by 50% or more with at least 5,000 B lymphocytes per microliter.
- 23. Transformation to a more aggressive histology (e.g., Richter syndrome). Whenever possible, this diagnosis should be established by lymph node biopsy.

Version 9, 18 Feb 2020

Table 8: Response Definition After Chronic Lymphocytic Leukemia Treatment

Parameter	CR*	PR*	₽D*
Group A	-	-	-
Lymphadenopathy†	None > 1.5 cm	Decrease ≥ 50%	Increase ≥ 50%
	None	Decrease ≥ 50%	Increase ≥ 50%
Splenomegaly	None	Decrease ≥ 50%	Increase ≥ 50%
Blood lymphocytes	<4000/μL	Decrease ≥ 50% from baseline	Increase ≥ 50% over baseline
	Normocellular, < 30% lymphocytes, no B lymphoid nodules. Hypocellular marrow defines CRi.	50% reduction in marrow infiltrate, or B lymphoid nodules	-
Group B	-	-	-
Platelet count	> 100 000/μL	> 100 000/μL or increase ≥ 50% over baseline	Decrease of ≥ 50% from baseline secondary to CLL
	> 11.0 g/dL	> 11 g/dL or increase ≥ 50% over baseline	Decrease of > 2 g/dL from baseline secondary to CLL
Neutrophils‡	> 1500/μL	>1500/µL or > 50% improvement over baseline	-

Note: Group A criteria define the tumor load, Group B criteria define the function of the hematopoietic system (or marrow).

Abbreviations: cm: Centimeter; Cri: CR with incomplete marrow recovery; dL: Deciliter; g: Gram; µL: Microliter Source: Hallek 2008.

1 LYMPHOMA

1.1 Tumor Assessment Criteria

The determination of response and progression for subject with NHL will be based on standardized criteria [Cheson 2014].

1.2 Method of Assessment

Imaging-based evaluation will be used in this study as the primary basis of lymphoma assessment. CT scan is the preferred method for radiographic tumor assessment. Contrast-

^{*} CR (complete remission): all of the criteria have to be met, and patients have to lack disease related constitutional symptoms; PR (partial remission): at least 2 of the criteria of group A plus one of the criteria of group B have to be met; SD is absence of progressive disease (PD) and failure to achieve at least a PR; PD: at least one of the above criteria of group A or group B has to be met.

[†] Sum of the products of multiple lymph nodes (as evaluated by CT scans in clinical trials, or by physical examination in general practice).

[‡] These parameters are irrelevant for some response categories.

Version 9, 18 Feb 2020

enhanced scanning is preferred, but contrast material may be omitted in subjects for whom use of a contrast agent becomes medically contraindicated or if CT scanning is done in conjunction with PET. If available, PET scan data will be considered in response and progression assessment; however, PET scanning will not be a required component of assessment in this study. As necessary, bone marrow aspirate/biopsy (e.g., for confirmation of CR) or cytological/histological evaluation of lymph nodes, effusions, ascites, or other organ abnormalities) will be also be considered. Clinical palpation, chest x-ray, ultrasound, endoscopy, laparoscopy, radionuclide scan, or tumor markers will not be considered for response assessment. MRI scanning is not advised but may be used at the investigator's discretion in subjects for whom this becomes a necessary alternative to CT scanning.

For radiographic assessments, the same method of assessment and the same technique (e.g., scan type, scanner, subject position, dose of contrast, injection/scan interval) should be used to characterize each identified and reported lesion at baseline and during study treatment and follow-up. CT of the neck, chest, abdomen, and pelvis should be performed with cuts of ≤ 0.5 mm in slice thickness contiguously. If performed, whole-body FDG PET-CT scanning should be extended from the base of the skull to mid-thigh.

All relevant radiographic and clinical information required to make each tumor status assessment must be made available for source verification as requested by the study sponsor.

1.3 Timing of Assessments

During screening, clinical and imaging-based tumor assessments should be performed within the specified screening period. On-study tumor assessments should be performed as stipulated in Section Changed. An end-of-therapy tumor assessment should be performed unless the subject already has radiographic confirmation of disease progression ≤ 4 weeks prior to study drug discontinuation. If a subject permanently discontinues treatment prior to objective documentation of lymphoma progression, investigators should ideally continue further follow-up of tumor status with assessments at ~ 12 -week intervals until disease progression is documented or until the initiation of a new post-study therapy for the subject's lymphoma.

1.4 Identification and Follow-up of Tumor Lesions and Organomegaly

1.4.1 Index Lesions

Up to 6 lesions (e.g., lymph nodes, liver or spleen nodules, and/or other circumscribed extranodal masses) should be selected as index lesions that will be used to quantitate the status of the disease during study treatment. Ideally, the index lesions should be located in disparate regions of the body and include mediastinal, abdominal, and retroperitoneal areas of disease whenever these sites are involved. For subjects with FDG-avid lymphomas undergoing PET, selection of FDG-avid lesions is preferred.

Index lesions will be measured and recorded at baseline and at the stipulated intervals during treatment. The largest cross-sectional dimensions (i.e., the $LD \times LPD$ will be recorded (in cm) for each index lesion. Using the LD and LPD, the product of the perpendicular diameters (PPD) for each index lesion will be calculated. The PPDs and the SPDs for all index lesions will be calculated and recorded. The baseline and nadir PPDs of individual lesions and the baseline and nadir SPDs will be used as references by which

Version 9, 18 Feb 2020

objective tumor response and progression will be characterized during treatment. All PPD and SPD measurements will be reported in centimeters squared.

1.4.2 Nodal Index Lesions

A nodal mass may be selected as a nodal index lesion if it is both abnormal and measurable at baseline. A lymph node lesion is considered abnormal if it has a single diameter that is > 1.0 cm and is considered measurable if it has 2 perpendicular diameters that can be accurately measured in cross section with the LD being ≥ 1.0 cm and the LPD also being ≥ 1.0 cm.

Abnormal, measurable nodal lesions will be subcategorized as either large or small.

- Large nodal lesions have an LD that is > 1.5 cm and an LPD that is ≥ 1.0 cm.
- Small nodal lesions have an LD that is > 1.0 cm and ≤ 1.5 cm and an LPD that is > 1.0 cm.

Index lesions measuring > 1.5 cm in the LD, regardless of the measurement of the LPD, will be prioritized during baseline index lesion selection.

At follow-up timepoints, the PPDs for individual nodal lesions and the SPD of all nodal index lesions will be considered. Because nodal index lesions that have one or both diameters > 0 cm and < 1.0 cm cannot be reliably measured, a default value of 1.0 cm will be assigned for each diameter that meets these criteria and the resulting PPD will be used in SPD calculations. Based on this convention, a CR may be achieved even if an SPD value is > 0 cm² (i.e., if all lymph nodes measure < 1.0 cm²).

New or enlarging nodal lesions that are still ≤ 1.0 cm by ≤ 1.0 cm will not be considered to represent recurrent or PD. A new node that measures > 1.5 cm in any diameter or a new node that measures > 1.0 cm to ≤ 1.5 cm in the LD and measures > 1.0 cm in the LPD will be considered PD.

In cases in which a large lymph node mass has split into multiple components, only those elements that are > 1.0 cm in ≥ 1 diameter will be considered abnormal and used in calculating the SPD. Components that are ≤ 1.0 cm in the LD are assumed to be normal lymph node structures. PD will not be based on the growth of a lesion sub-component until it meets the criteria for abnormal. Lesion sub-components that are abnormal (> 1.0 cm in ≥ 1 diameter) will have the true PPDs calculated with the result used only for calculating an accurate nadir. Lesion subcomponents that are normal (≤ 1.0 cm in the LD) will have the default PPD of 1.0 cm 2 (1.0 cm x 1.0 cm) stored only for the purposes of calculating the nadir value.

If lesions merge, a boundary between the lesions will be established so the LD of each individual lesion can continue to be measured. If the lesions have merged in a way that they can no longer be separated by this boundary, the newly merged lesion will be measured bidimensionally.

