1.4.3 Extranodal Index Lesions

An extranodal mass may be selected as an index lesion if it is both abnormal and measurable at baseline. An extranodal mass of any size is considered abnormal. It is considered measurable at baseline if it has 2 perpendicular diameters that can be

Version 9, 18 Feb 2020

accurately measured in cross section with the LD being \geq 1.0 cm and the LPD also being \geq 1.0 cm.

At follow-up timepoints, the PPD of each single extranodal index lesion and the SPD of all extranodal index lesions will be considered. Because extranodal index lesions that have one or both diameters < 0.5 cm and > 0 cm cannot be reliably measured, a default value of 0.5 cm will be assigned for each diameter that meets these criteria and the resulting PPD will be used in SPD calculations. If an extranodal lesion is no longer clearly visible, it will be considered resolved and its PPD will be defined as 0 cm^2 .

If an extranodal lesion that had resolved (i.e., had a PPD of 0 cm²) subsequently reappears, the subject will be considered to have PD. A new extranodal lesion of any size that appears at a site that was not previously involved with lymphoma and is discernible to the radiologist by CT scan will be considered PD.

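### The 1.0 cm default for small nodal diameters equals the minimum entry short axis, so it can mask a partial response in subjects with small or narrow index nodes

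*Combined protocol and SAP*

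**What the plan says.** Appendix 2 (criteria for response assessment) appears in the amendment log as replacement text.

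- **Entry, section 1.4.2.** A nodal index lesion is measurable "with the LD being ≥ 1.0 cm and the LPD also being ≥ 1.0 cm". The small-node class is defined separately: "Small nodal lesions have an LD that is > 1.0 cm and ≤ 1.5 cm and an LPD that is > 1.0 cm".
- **Follow-up, section 1.4.2.** The text states that "nodal index lesions that have one or both diameters > 0 cm and < 1.0 cm cannot be reliably measured", and therefore that "a default value of 1.0 cm will be assigned for each diameter that meets these criteria". The resulting product (PPD) enters the SPD. A diameter of 0 cm is not affected.
- **CLL/SLL, section 2.4.1.** The same entry minimum and the same 1.0 cm default apply.
- **Extranodal lesions, section 1.4.3.** Here "a default value of 0.5 cm will be assigned for each diameter that meets these criteria".
- **Response, sections 1.5.1 to 1.5.3.** PR needs an SPD fall of at least 50% from baseline. CR uses node size instead: long diameter (LD) at most 1.5 cm for large nodes, and longest perpendicular diameter (LPD) at most 1.0 cm for small ones. SD is what remains when neither PR nor PD is met. Section 1.4.2 acknowledges that CR is possible with a non-zero SPD.
- **Recording, section 1.4.1.** LD and LPD are recorded for each index lesion.

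**The concern.** A response measure should be able to move from its entry value. Here a node may enter with an LPD of 1.0 cm, and any later LPD that is visible but smaller is written back to 1.0 cm. That axis can then register no shrinkage until the node vanishes. The same floored products feed the nadir, so regrowth back up to 1.0 cm is invisible too.

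The objective response rate (ORR) is at stake. In section 14.1.2 the follicular lymphoma cohorts are judged against responder-count boundaries in at most about 20 evaluable subjects, and the cohorts of six against a result of 0/6. At those sizes a single reclassified subject can change the conclusion.

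**Working it through.** **Inputs.** Default 1.0 cm for diameters above 0 and below 1.0 cm (1.4.2, 2.4.1); entry LPD at least 1.0 cm (1.4.2); PR at an SPD fall of 50% or more (1.5.2); CR node sizes (1.5.1); eligibility lesion at least 2.0 × 1.0 cm (inclusion criterion 4). The node sizes below are illustrative assumptions. Subjects are taken to be followed by CT, because section 1.5 lets metabolic criteria take precedence when assessing CR in FDG-avid tumors.

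**Plan's own figure.** The default product is 1.0 × 1.0 = 1.0 cm², as stated.

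**Rule.** Scored diameter = 0 if the node is gone, otherwise the larger of the measured diameter and 1.0 cm. PPD = LD × LPD; SPD = sum of PPDs; fall = 1 − SPD(follow-up)/SPD(baseline).

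**Limits for a single visible node with baseline PPD = P (cm²).**
- The smallest scored PPD is 1.0, so the largest fall that can register is 1 − 1/P. Below P = 2.0 it cannot reach 50%. For 1.3 × 1.1 cm, P = 1.43 and the maximum is 30.1%.
- If LD stays above 1.5 cm and LPD drops below 1.0 cm, the scored PPD equals LD, which exceeds 1.5. The fall is then less than 1 − 1.5/P, so any P of 3.0 or below cannot reach 50%.

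**Cases scored SD despite a true fall of at least 50%.** In each, one LD is above 1.5 cm, so CR also fails.

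| Baseline → follow-up (cm) | True fall | Scored fall |
|---|---|---|
| 3.0×1.0 → 1.6×0.5 | 1 − 0.80/3.00 = 73% | 1 − 1.60/3.00 = 47% |
| 2.0×1.0 → 1.6×0.6 | 1 − 0.96/2.00 = 52% | 1 − 1.60/2.00 = 20% |
| 2.5×1.2 → 1.8×0.8 | 1 − 1.44/3.00 = 52% | 1 − 1.80/3.00 = 40% |
| 2.0×1.0 and five 1.3×1.1 → 1.6×0.9 and five 0.7×0.7 | 1 − 3.89/9.15 = 57.5% | 1 − 6.60/9.15 = 27.9% |

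With a 0.5 cm default the scored fall equals the true fall in all four.

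**Cases where the rule does little or no harm.**
- 2.0×1.0 → 0.9×0.9: true 59.5%, scored 50.0%. The PR threshold is still met.
- 3×2 and two 2×1.5 → 1.8×1.2 and two 0.9×0.8: 70.0% against 65.3%, PR either way.
- 5×4 → 3×2.5: 62.5% either way.
- A node that disappears scores 100%.
- A small node, 1.4×1.2 → 0.8×0.7: true 66.7%, scored 40.5%, but it meets the CR node-size criterion. The fall is lost only if another CR criterion is unmet.

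**Weight of one responder.** The boundary of 8/20 in section 14.1.2 is said to give a one-sided 95% lower bound of at least 20%. The exact bound, the 5% quantile of Beta(8, 13), is 21.7%, which agrees. For 7/20, Beta(7, 14) gives 17.7%, below 20%.

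**How often?** The results depend on assumptions and denominators.
- A single-node grid (LD from 2.0 cm up to 3, 4 or 6 cm, proportional shrinkage) masks 2.2% to 2.8% of all grid points with a true fall of at least 50%.
- A three-node simulation (linear shrinkage 20–50%, axis ratio 0.45–0.9), restricted to true falls of at least 50% with a node still above 1.5 cm, masks 39%, 15% and 5% when baseline nodes are at most 2.5, 3 and 4 cm. With a 0.5 cm default it masks 0%.

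None of these is a patient rate.

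**The case against.** The strongest defence is that the nodal default follows the appendix's own idea of a normal node. Section 1.4.2 treats components of 1.0 cm or less as normal node structure and does not count nodes within 1.0 × 1.0 cm as progression, whereas section 1.4.3 treats an extranodal mass of any size as abnormal. Two definitions of abnormal can justify two floors. This stands in part: the 0.5 cm extranodal rule does not by itself prove the nodal rule wrong. It does not answer the table above, where a node with LD 1.6 cm is still abnormal and only its short axis is floored.

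A second defence is that CR bypasses SPD. That rescues subjects whose index nodes all reach normal size, but only if non-index disease, spleen, liver and marrow also qualify. Where marrow involvement is the only obstacle, the last PR bullet in section 1.5.2 may still give PR, so that situation is not relied on here.

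A third is that the rule errs against the drug, and that loosening it after responses have been seen would be a post hoc change in favour of ORR. That stands, and it shapes the fix.

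A reader might also cite the older response table in the same log, which says "When a lesion is too small to measure on CT, assign 5 mm × 5 mm as the default value". That table is superseded, so the difference is not an error and carries no weight here.

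**Conclusion.** The point holds in a limited form. Followed exactly, the rule can turn a true SPD fall of 50% or more into SD when baseline SPD is low, when a node keeps LD above 1.5 cm while its LPD drops below 1.0 cm, or when nodes reach normal size but another CR criterion is unmet. In the worked cases the scored fall is 12 to 32 percentage points short of the true one.

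A reader might infer that true partial responses are generally scored as SD, or that ORR is biased downward by a known amount. The documents do not support either. A diameter of 0 cm is exempt, shrinkage down to 1.0 cm registers in full, bulky disease is barely affected, and no node-size distribution is given. The simulated percentages rest on assumed sizes.

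One limit remains: the wording reviewed is the replacement text in the amendment log. The current Appendix 2 is in the part of the document not shown. No later change to this rule appears in the logs that are shown.

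**What to change.** In sections 1.4.2 and 2.4.1, compute nodal SPD and nadir from the recorded diameters and assign 0.5 cm to any smaller visible diameter, as section 1.4.3 does for extranodal lesions. Align the 1.0 × 1.0 cm sub-component nadir defaults in both sections, and the sentence explaining how CR can coexist with a non-zero SPD.

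If responses have already been scored under the 1.0 cm rule, keep that as the reported ORR. Add the 0.5 cm version as a labelled sensitivity analysis of ORR and of the accrual boundaries in section 14.1.2. This is the likelier route: the latest logged changes provide for closing Stages 1 and 2 and locking the database.

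While editing, reconcile the measurability minimum with the statement that index lesions above 1.5 cm in LD, "regardless of the measurement of the LPD, will be prioritized during baseline index lesion selection". The default is stated for follow-up only. If a 2.0 × 0.6 cm node were indexed and did not change, its PPD would go from 1.2 to 2.0 cm², a scored rise of 67%, past the 50% SPD progression threshold.

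The cost is appendix wording, derivation code and one extra table. The downside is slightly noisier SPD for nodes of 0.5–1.0 cm.
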